7.4.2. Concomitant Medications

Concomitant medications are defined as medications taken while a subject is on study drug, regardless of when the medication was started. Use of general and disease-specific concomitant medications will be summarized by preferred name using the number and percentage of subjects for each treatment group. A subject reporting the same medication more than once will be counted only once when calculating the number and percentage of subjects who received that medication. The summary will be ordered alphabetically by preferred term in descending overall frequency. For drugs with the same frequency, sorting will be done alphabetically.

For the purposes of analysis, any medications with a start date prior to or on the first dosing date of study drug and continued to be taken after the first dosing date, or started after the first dosing date but prior to or on the last dosing date of study drug will be considered concomitant medications. Medications started and stopped on the same day as the first dosing date or the last dosing date of study drug will also be considered concomitant. Medications with a stop date prior to the date of first dosing date of study drug or a start date after the last dosing date of study drug will be excluded from the concomitant medication summary. If a partial stop date is entered, any medication with the month and year (if day is missing) or year (if day and month are missing) prior to the date of first study drug administration will be excluded from the concomitant medication summary. If a partial start date is entered, any medication with the month and year (if day is missing) or year (if day and month are missing) after the study drug stop date will be excluded from the concomitant medication summary.

Medications with completely missing start and stop dates will be listed but not included in the concomitant medication summary, unless the medication is reported as ongoing.

In addition, prior and concomitant medications for SjS, SLE and RA will be presented in a separate summary table by medication category (csDMARD, systemic corticosteroids, other corticosteroids, NSAIDs, anti-malarial drugs and other), and preferred term.

All prior and concomitant medications (other than per-protocol study drugs) will be provided in a by-subject listing sorted by subject ID number and administration date in chronological order based on Safety Analysis Set.

Summaries will be based on the Safety Analysis Set. No formal statistical testing is planned.

7.5. Electrocardiogram Results

A shift table of the investigators' assessment of ECG results at each visit compared with baseline values will be presented by treatment group using the following categories: normal; abnormal, not clinically significant; abnormal, clinically significant; or missing. The number and percentage of subjects in each cross-classification group of the shift table will be presented. Subjects with a missing value at baseline or postbaseline will not be included in the denominator for percentage calculation. No formal statistical testing is planned.

A by-subject listing for ECG assessment results will be provided by subject ID number and visit in chronological order.

7.6. Other Safety Measures

A data listing will be provided for subjects who become pregnant during the study.

7.7. Changes From Protocol-Specified Safety Analyses

There are no deviations from the protocol-specified safety analyses.

8. PHARMACOKINETIC (PK) ANALYSES

Plasma concentrations of filgotinib, the active metabolite of filgotinib (GS-829845), lanraplenib and tirabrutinib will be listed and summarized using descriptive statistics (eg, sample size, arithmetic mean, geometric mean, % coefficient of variation, standard deviation, median, minimum, and maximum).

CCI

8.1. Pharmacokinetic Sample Collection

PK samples will be collected prior to study drug administration (pre-dose) at Weeks 4, 8, 12, 24, 36, and 48/ET visit. At Week 18, PK samples will be collected approximately 2 hours post-dose. CCI

8.2. PK Analyses Related to Intensive PK Sampling

CCI

8.3. Estimation of Pharmacokinetic Parameters

PK parameters will be estimated using Phoenix WinNonlin[®] software using standard noncompartmental methods. The linear/log trapezoidal rule will be used in conjunction with the appropriate noncompartmental model, with input values for dose level, dosing time, plasma concentration, and corresponding real-time values, based on drug dosing times whenever possible.

For area under the curve (AUC), samples BLQ of the bioanalytical assays occurring prior to the achievement of the first quantifiable concentration will be assigned a concentration value of 0 to prevent overestimation of the initial AUC. Samples that are BLQ at all other time points will be treated as missing data in WinNonlin. The nominal time point for a key event or dosing interval (τ) may be used to permit direct calculation of AUC over specific time intervals. The appropriateness of this approach will be assessed by the PK scientist on a profile-by-profile basis.

Pharmacokinetic parameters such as AUC_{τ} , λ_z and $t_{1/2}$ are dependent on an accurate estimation of the terminal elimination phase of drug. The appropriateness of calculating these parameters will be evaluated upon inspection of PK data on a profile-by-profile basis by the PK scientist.

8.4. Pharmacokinetic Parameters

CCI

Table 4. Study Treatments and Associated Analytes

Treatment	Analyte
Filgotinib 200 mg	Filgotinib, GS-829845
Lanraplenib 30 mg	Lanraplenib
Tirabrutinib 40 mg	Tirabrutinib

The analytes and parameters presented in Table 5 will be used to evaluate the PK objectives of the study. The primary PK parameters are AUC_{τ} , C_{τ} , and C_{\max} of filgotinib, and active metabolite of filgotinib (GS-829845), lanraplenib and tirabrutinib. The PK parameters to be estimated in this study are listed and defined in the Pharmacokinetic Abbreviations section.

Table 5. Pharmacokinetic Parameters for Each Analyte

Analyte	Parameters
Filgotinib	AUC_{τ} , C_{τ} , C_{\max} , T_{\max} , λ_z , CL/F, Vz/F and $t_{1/2}$, if appropriate
GS-829845	AUC_{τ} , C_{τ} , C_{\max} , T_{\max} , λ_z , and $t_{1/2}$, if appropriate
Lanraplenib	AUC_{τ} , C_{τ} , C_{\max} , T_{\max} , λ_z , CL/F, Vz/F and $t_{1/2}$, if appropriate
Tirabrutinib	AUC_{τ} , C_{τ} , C_{\max} , T_{\max} , λ_z , CL/F, Vz/F and $t_{1/2}$, if appropriate

8.5. Statistical Analysis Methods

Individual subject concentration data and individual subject PK parameters for filgotinib, GS-829845, lanraplenib and tirabrutinib will be listed and summarized using descriptive statistics by treatment. Summary statistics (number [n], mean, SD, coefficient of variation [%CV], median, min, max, Q1, and Q3) will be presented for both individual subject concentration data by time point and individual subject PK parameters by treatment. Moreover, the geometric mean, 95% CI, and the mean and SD of the natural log-transformed values will be presented for individual subject PK parameter data.

Individual concentration data listings and summaries will include all subjects with concentration data. The sample size for each time point will be based on the number of subjects with nonmissing concentration data at that time point. The number of subjects with concentration

BLQ will be presented for each time point. For summary statistics, BLQ values will be treated as 0 at predose and one-half of the lower limits of quantitation (LLOQ) for postdose time points.

For Weeks 4, 8, 12, 24, 36, and 48/ET visit data, only samples collected 20 to 28 hours after the prior dose will be included in the summary statistics. For Week 18 data, only samples collected 1 to 4 hours after the administration of study drug on the visit day will be included in the summary statistics.

Individual PK parameter data listings and summaries will include all subjects for whom PK parameter(s) can be derived. The sample size for each PK parameter will be based on the number of subjects with nonmissing data for that PK parameter.

The following tables will be provided for each analyte by treatment:

- Individual subject concentration data and summary statistics
- Individual subject plasma PK parameters and summary statistics

The following figures may be provided for each analyte by treatment:

- Individual subject concentration data versus time (on linear and semilogarithmic scales)
- Mean (\pm SD) concentration data versus time (on linear and semilogarithmic scales)
- Median (Q1, Q3) concentration data versus time (on linear and semilogarithmic scales)

Individual, mean, and median postdose concentration values that are \leq LLOQ will not be displayed in the figures and remaining points connected.

The following listings will be provided:

- PK sampling details (and PK concentrations) by subject, including procedures, differences in scheduled and actual draw times, and sample age

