8.2.1.4. Pharmacokinetics

8.2.1.4.1. PK Substudy Analysis Set

8.2.1.4.2. PK Analysis Set

The primary analysis set for PK analyses will be the PK Analysis Set, which includes all subjects in the Safety Analysis Set who have at least 1 non-missing PK concentration data for GS-9876, filgotinib, GS-4059, and/or their metabolite(s).

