8.3. Data Handling Conventions

Pharmacokinetic concentration values and PK parameter values below the limit of quantitation (BLQ) will be presented as “BLQ” in the data listings. BLQ values that occur prior to the first dose will be treated as 0, BLQ values at all other time points will be treated as 1/2 of the lower limit of quantitation (LLOQ).

Laboratory data that are continuous in nature but are less than the lower limit of quantitation or above the upper limit of quantitation will be imputed to the value of the lower or upper limit minus or plus one significant digit, respectively (eg, if the result of a continuous laboratory test is < 20, a value of 19 will be assigned; if the result of a continuous laboratory test is < 20.0, a value of 19.9 will be assigned).

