3.1.5. Pharmacokinetic Analysis Set

The Pharmacokinetic (PK) Analysis Set will include all subjects in the Safety Analysis Set who have at least 1 non-missing post-dose PK concentration data for filgotinib, lanraplenib, tirabrutinib, and/or their metabolite(s). This is the primary analysis set for all PK analyses.

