3.8. Analysis Visit Windows

3.8.1. Definition of Study Day

Study day will be calculated from the first dosing date of study drug and derived as follows:

- For postdose study days: Assessment Date – First Dosing Date + 1
- For days prior to the first dose: Assessment Date – First Dosing Date

Therefore, study Day 1 is the day of first dose of study drug administration.

For placebo subjects who were re-randomized to active treatment, the On-Active-Treatment study day will be calculated as: Assessment Date – Date of the first dose of active treatment + 1. The date of the first dose of active treatment is recorded on CRF.

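### Does the SAP's zero rule for BLQ values at predose override the protocol's half-LLOQ rule for on-treatment troughs?

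*SAP*

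**What the plan says.** **BLQ rule.** For concentration summaries, SAP 8.5 states that "BLQ values will be treated as 0 at predose and one-half of the lower limits of quantitation (LLOQ) for postdose time points". Protocol 8.3 ties the zero to the start of dosing: "BLQ values that occur prior to the first dose will be treated as 0", and "BLQ values at all other time points will be treated as 1/2 of the lower limit of quantitation (LLOQ"). SAP 3.7 carries a parallel rule that sets predose (value 0) against postbaseline (half the LOQ).

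**How the SAP uses the words elsewhere.** SAP 8.1 applies the label to visits during treatment: "PK samples will be collected prior to study drug administration (pre-dose) at Weeks 4, 8, 12, 24, 36, and 48/ET visit". It adds: "At Week 18, PK samples will be collected approximately 2 hours post-dose". SAP 3.8.1, by contrast, counts from the first dosing date ("For postdose study days: Assessment Date" and so on) and opposes this to days before the first dose. SAP 3.1.5 admits to the PK Analysis Set subjects with "at least 1 non-missing post-dose PK concentration data for filgotinib, lanraplenib, tirabrutinib, and/or their metabolite(s"), where Protocol 8.2.1.4.2 asks only for "at least 1 non-missing PK concentration data for GS-9876, filgotinib, GS-4059, and/or their metabolite(s").

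**Draw time.** Protocol 6.16.4 has pre-dose PK draws at Weeks 4, 12 and 24 but leaves the time open, relative to the last dose, at Weeks 8, 36 and 48/ET. Protocol 5.7, Protocol Appendix 2 footnote p and SAP 8.1 put the draw before the dose at all six visits. The visit sections for Week 8 (6.6) and Week 36 (6.12) agree with them.

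**The concern.** Six of the seven unredacted PK visits carry the label pre-dose in SAP 8.1, and the protocol glossary also describes the trough as a pre-dose sample. A programmer who takes the label at face value would replace every BLQ trough with 0 during treatment, against Protocol 8.3. That would lower the mean and inflate the SD and %CV at those visits. The same reading would reach two other places. In SAP 3.1.5, only the Week 18 sample would qualify a subject for the PK Analysis Set. In the SAP 8.5 figure rule, which hides only postdose values at or below LLOQ, troughs set to zero would stay on semilogarithmic plots, where they cannot be drawn.

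The draw-time mismatch looks like a second route to trouble. SAP 8.5 keeps only samples taken 20 to 28 hours after the prior dose at the six trough visits, so a draw after the clinic dose, which 6.16.4 seems to allow, would normally drop out of the summaries.

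**Working it through.** The documents state no figure to reproduce, so the check is textual, followed by arithmetic for scale.

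**1. Test each reading against the rest of the plan.**

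| Passage | Predose = before that visit's dose | Predose = before the first dose |
|---|---|---|
| Protocol 8.3 | contradicts it for every trough | agrees |
| SAP 3.7, BLQ rule | a Week 12 trough is both predose (0) and postbaseline (half LOQ) | one value per sample |
| SAP 3.8.1 | postdose has a different meaning here | same meaning |
| SAP 3.1.5 | 1 of 7 visible PK visits can qualify a subject | all 7 can |
| SAP 3.7 (log transform), SAP 8 and Protocol 8.7 (geometric mean of concentrations) | not computable with a zero | computable |
| SAP 3.7, BLQ PK parameters at half LOQ | a BLQ trough could be 0 as a concentration and half LOQ as C~tau~ | no clash |
| SAP 8.1 label | same use of the word | different use of the word |

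Only the SAP 8.1 label favours the first column, and it describes when blood is drawn, not how values are imputed. SAP 8.5 itself describes the trough samples as taken 20 to 28 hours after the prior dose, so they follow dosing.

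**2. Size if someone did use the first reading.** For n values at a visit, f of them BLQ:

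difference in arithmetic mean = (f/n) × (LLOQ/2 − 0)

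n = 35 is the planned arm size (Protocol 3.2). The BLQ counts and concentration levels are assumptions, since the documents give none. If all quantifiable values equal g × LLOQ, the mean with zeros is (n − f)g/n, and the relative difference is 0.5f / ((n − f)g).

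| f of 35 | Difference (LLOQ units) | Relative, g = 5 | Relative, g = 10 to 2 |
|---|---|---|---|
| 4 | 4/35 × 0.5 = 0.057 | 2/155 = 1.3% | 0.6% to 3.2% |
| 9 | 9/35 × 0.5 = 0.129 | 4.5/130 = 3.5% | 1.7% to 8.7% |
| 18 | 18/35 × 0.5 = 0.257 | 9/85 = 10.6% | 5.3% to 26.5% |

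For f = 9 and g = 5, the mean is 3.714 or 3.843 LLOQ and the %CV 59.7 or 51.9. The larger differences need many BLQ values, and there the output already warns the reader. SAP 8.5 reports the number of BLQ subjects at each time point. SAP 3.7 shows the minimum as BLQ from one such value, Q1 above 25% (9/35 = 25.7%) and the median above 50% (18/35 = 51.4%).

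**3. Week 24 samples of subjects re-randomised from placebo.** These precede the first active dose, in about 35/3 ≈ 12 subjects per drug before dropout. SAP Table 1 keeps these subjects on placebo until the Week 24 first dose, SAP 3.2 groups the PK set by treatment actually received, and SAP Table 4 lists no analyte for placebo. No visible text brings these samples into an active-drug summary, so no extra rule is needed.

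**4. Draw time.** A pre-dose draw at Weeks 8, 36 and 48/ET satisfies 5.7, footnote p, SAP 8.1 and the open wording of 6.16.4, and at Weeks 8 and 36 also 6.6 and 6.12. A post-dose draw satisfies only 6.16.4.

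**The case for a change.** The best argument for a change is that the visible PK schedule starts at Week 4 with no Day 1 sample. If predose means before the first dose, the zero rule has almost nothing visible to act on, which might suggest that it was written for troughs. The contrast in SAP 3.7 is also not a formal definition, because a trough is both predose and postbaseline. And under a lognormal model with true CV 50% and 30% of values BLQ, the mean falls by 11.1% and the reported %CV rises from 58.4 to 80.2.

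The first point has some force but does not decide the matter. The intensive PK text in SAP 8 is redacted and may contain the samples the zero was meant for, and a rule with few samples to act on does no harm. On the second, a reading that assigns two values to one sample should give way to the reading that assigns one. The third depends on an assumed LLOQ very close to typical troughs. With s = √ln(1 + 0.5²) = 0.472, the 30% quantile lies at exp(−0.524 × 0.472) ≈ 0.78 of the median trough. Nothing in the documents suggests levels that near the assay limit.

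What stands is that the word is undefined, and that Protocol 6.16.4 is worded more loosely than the passages it should match.

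**Conclusion.** No change to the plan is needed. The SAP leaves a term undefined, and the reading that agrees with Protocol 8.3 is the only one that fits SAP 3.7, 3.8.1, 3.1.5 and the log-scale summaries of concentrations. An analyst following the plan would use half the LLOQ for on-treatment troughs, so rewording would only record what will be done anyway. If the other reading slipped in, a visit's mean would move by (f/n) × LLOQ/2: 1.3% with 4 of 35 values BLQ and 3.5% with 9, assuming quantifiable values of 5 × LLOQ. The effect stays within descriptive PK output, next to a reported BLQ count. No hypothesis test, efficacy result, sample size or stated figure depends on it.

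The draw-time difference is a clerical slip. The passages should be reconciled whenever the protocol is next edited, but sites that follow the dosing section and the schedule footnote already draw before the dose, the SAP 8.5 window handles off-time samples, and no loss of data is shown. The conclusion rests on the visible text; the redacted intensive-sampling sections could not be checked.

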10. SOFTWARE

SAS[®] Software Version 9.4. SAS Institute Inc., Cary, NC, USA.

nQuery Advisor(R) Version X.0. Statistical Solutions, Cork, Ireland.

11. SAP REVISION

Revision Date (DD MMM YYYY)	Section	Summary of Revision	Reason for Revision

12. APPENDIXES

Appendix 1. Schedule of Assessments

	Screening ^a	Day 1 ^b	Week 2	Week 4	Week 8	Week 12	Week 18	Week 24	Week 26	Week 28	Week 32	Week 36	Week 42	Week 48/ET ^c	Follow Up visit 4 weeks after subject's last study visit ^d
Visit window	None	None	+/- 3 days	+/- 3 days	+/- 3 days	+/- 3 days	+/- 3 days	+/- 3 days	+/- 3 days	+/- 3 days	+/- 3 days	+/- 7 days	+/- 7 days	+/- 7 days	+/- 7 days
Fasting visit		x				X		x						x	
IP to be taken at the clinic		x	x	x	x	X	x	x	x	x	x	x	x	x	
Written Informed Consent	x														
Randomization		x ^e						x ^f							
Physical exam and provider assessments															
SjS medical/surgical history, including diagnosis and prior treatments,	x														
Medical /Surgical History (non-SjS)	x														
Vital Signs, including weight and height ^g	x	x	x	x	x	X	x	x	x	x	x	x	x	x	x
Complete Physical Examination	x							x						x	
Symptom-directed PE		x	x	x	x	X	x		x	x	x	x	x		x
ESSDAI	x	x ^y		x	x	X	x	x		x	x	x	x	x	
PE for domains of ESSDAI ^h	x	x		x	x	X	x	x		x	x	x	x	x	
28 Swollen and Tender Joint count	x	x	x	x	x	X	x	x	x	x	x	x	x	x	

	Screening ^a	Day 1 ^b	Week 2	Week 4	Week 8	Week 12	Week 18	Week 24	Week 26	Week 28	Week 32	Week 36	Week 42	Week 48/ET ^c	Follow Up visit 4 weeks after subject's last study visit ^d
Visit window	None	None	+/- 3 days	+/- 3 days	+/- 3 days	+/- 3 days	+/- 3 days	+/- 3 days	+/- 3 days	+/- 3 days	+/- 3 days	+/- 7 days	+/- 7 days	+/- 7 days	+/- 7 days
Physician's Global Assessment of SjS activity	x	x	x	x	x	X	x	x	x	x	x	x	x	x	x
Physician's Global Assessment of concomitant RA or SLE disease activity as applicable	x	x	x	x	x	X	x	x	x	x	x	x	x	x	x
Laboratory assessments															
Urine drug screen ⁱ	x														
Urinalysis with spot protein/microalbumin/creatinine	x	x	x	x	x	X	x	x	x	x	x	x	x	x	
Urine Pregnancy Test (female subjects of child bearing potential only)		x	x	x	x	X	x	x	x	x	x	x	x	x	x
Urine for biomarker (fasting)		x				X		x						x	
Serum Pregnancy Test (female subjects of child bearing potential) or FSH	x														
TB testing ^j	x														
CD19+ B cell count ^k	x														
HbA1c, TSH	x														
Hematology, ESR as applicable, chemistry and hsCRP	x	x	x	x	x	X	x	x	x	x	x	x	x	x	x
Viral Screening and Reflex PCR ^l	x														
Viral Monitoring ^m						X		x				x		x	

[figure not shown]
	Screening ^a	Day 1 ^b	Week 2	Week 4	Week 8	Week 12	Week 18	Week 24	Week 26	Week 28	Week 32	Week 36	Week 42	Week 48/ET ^c	Follow Up visit 4 weeks after subject's last study visit ^d
Visit window	None	None	+/- 3 days	+/- 3 days	+/- 3 days	+/- 3 days	+/- 3 days	+/- 3 days	+/- 3 days	+/- 3 days	+/- 3 days	+/- 7 days	+/- 7 days	+/- 7 days	+/- 7 days
Autoantibodies ⁿ	x	x				X		x						x	
Complement (C3, C4, CH50), and CK	x	x	x	x	x	X	x	x	x	x	x	x	x	x	
Cryoglobulins, total Ig, quant IgG, IgA, and IgM, serum and urine immunofixation	x			x		X		x		x		x		x	
Lipid profile (fasting) ^o		x				X		x						x	
PK samples ^p				x	x	X	x	x				x		x	
CCI															
Blood for Biomarker samples ^f	x	x	x	x	x	X	x	x	x	x	x	x	x	x	x
CCI															
PROs and questionnaires															
VAS ^t	x	x	x	x	x	X	x	x	x	x	x	x	x	x	x
ESSPRI	x	x	x	x	x	X	x	x	x	x	x	x	x	x	x
FACIT- Fatigue, OHIP-14, PROFAD-SSI-SF ^u		x		x	x	X	x	x		x	x	x	x	x	
SF-36, IDEEL ^u		x				X		x				x		x	
TSQM		x				X		x				x		x	
Cognitive testing		x		x	x	X	x	x		x	x	x	x	x	

	Screening ^a	Day 1 ^b	Week 2	Week 4	Week 8	Week 12	Week 18	Week 24	Week 26	Week 28	Week 32	Week 36	Week 42	Week 48/ET ^c	Follow Up visit 4 weeks after subject's last study visit ^d
Visit window	None	None	+/- 3 days	+/- 3 days	+/- 3 days	+/- 3 days	+/- 3 days	+/- 3 days	+/- 3 days	+/- 3 days	+/- 3 days	+/- 7 days	+/- 7 days	+/- 7 days	+/- 7 days
Procedures and Exams															
12-Lead ECG	x	x	x		x	x		x	x		x	x		x	x
Pulmonary function tests ^v	x					x		x						x	
CCI															
Chest X-ray (as applicable) ^z	x														
CCI															
Drug dispensing		x		x	x	x	x	x		x	x	x	x		
Drug accountability			x	x	x	x	x	x	x	x	x	x	x	x	
Adverse Events	x	x	x	x	x	x	x	x	x	x	x	x	x	x	x
Concomitant medications ^x	x	x	x	x	x	x	x	x	x	x	x	x	x	x	x

- a Screening window is 28 days prior to Day 1
- b Subject will begin study drug on Day 1, following baseline assessments and randomization.
- c Early Termination Visit to be performed if subject discontinues before Week 48
- d Follow up visit not needed if subject's last dose of study drug was >4 weeks prior to their last study visit
- e Subjects will be randomized on Day 1 based on their use of concomitant medications (y/n: csDMARD and/or oral corticosteroid) and ESSDAI hematological plus biological domains score at Day 1, (Y/N: ESSDAI ≥ 2).
- f Subjects on placebo will be re-randomized 1:1:1 to either filgotinib, or GS-9876 or GS-4059
- g Height is only required at Visit 1 and subjects are to remove shoes during measurement
- h Exam should include glandular exam, lymph nodes, general skin, neurologic exam for peripheral neuropathy, pulmonary exam

- i Amphetamines Cocaine, Methadone Opiates
- j Quantiferon gold
- k As applicable
- l Hepatitis B surface Ag and core Ab, Hepatitis C Ab, reflex HCV RNA, HIV 1 and 2 at Screening
- m Viral monitoring for HCV as applicable (see study protocol.)
- n At screening only: anti SSA and anti SSB
At Day 1: deamidated gliadin peptide antibodies (anti-DGP IgA or IgG); Anti-endomysial antibodies (EMA), RF, CCP, dsDNA, ANA, IgA anti-tTA (tissue transglutaminase antibodies),
At all subsequent time points: deamidated gliadin peptide antibodies (anti-DGP IgA or IgG); Anti-endomysial antibodies (EMA), RF, CCP, dsDNA, ANA, SSA, SSB, IgA anti-tTA (tissue transglutaminase antibodies),
- o As outline in protocol Appendix 6
- p PK samples will be collected prior to study drug administration (pre-dose) at Weeks 4, 8, 12, 24, 36, and 48/ET visit. At Week 18, PK samples will be collected approximately 2 hours post-dose
- q CCI [REDACTED]
- r Inflammation and Pathway Biomarkers, RNA Sample, Whole Blood Sample for MoA Studies. For biomarkers which require specific material for sampling and/or processing, to be done if and when the material is available at site.
- s CCI [REDACTED]
- t Visual analog scales include patient global assessment of SJS activity and concomitant RA, concomitant SLE disease activity as applicable, assessment of ocular, oral dryness, vaginal dryness (if applicable) assessment of pain, fatigue, CCI [REDACTED],
- u If available in the primary language of the subject. Questionnaires addressing disease, activity and fatigue may be provided when and where available.
- v PFT includes Spirometry. Subjects with the following contraindications to spirometry should not perform the exam: nausea, vomiting, recent stroke, eye surgery, thoracic/abdominal surgery and recent pneumothorax
- w CCI [REDACTED]
- x All non-SjS medication used within 30 days of consent (including any changes) is to be documented in the eCRF.
All prior medication(s) used in the treatment for SjS, are to be documented in the eCRF
- y For ESSDAI at baseline, lab results and PFT from screening will be used
- z For subject who had no previous chest X-ray available for review by the investigator within the last 3 months

